3.3.2 Rationale for Open-Label Study

The primary endpoint of the study is OS, and an open-label design would have minimal impact on OS. Given that this study is being conducted in a patient population with almost no treatment options that could affect the endpoints of the study, an open-label study design is unlikely to impart a significant bias to the study results. Furthermore, the study utilizes three study drugs with two administration routes and schedules, which introduces substantial challenges to blinding and can result in erroneous drug administration.

3.3.3 Rationale for Patient Population, Stratification Factors, and Capping

The Phase Ib trial (GP28363) evaluated the cobimetinib and atezolizumab in KRAS-mutated mCRC patients and demonstrated promising clinical activity (Section 1.7). RAS-mutated mCRC, in general, have a relatively poor immune cell infiltration and low immune inhibitory molecule expression compared to RAS wild-type colorectal tumors (Lal et al. 2015).

The proposed mechanism of action would predict that this combination would be just as effective or potentially more efficacious in patients with RAS-wild type mCRC who generally have a more favorable tumor immune microenvironment. Therefore, given the promising clinical activity and high unmet need, this Phase III study will include both RAS mutant and RAS wild-type mCRC patients.

This Phase III study will stratify patients based on their tumor extended RAS mutation status and time since diagnosis of first metastasis. These are important predictive and prognosis factors for mCRC and may potentially affect treatment outcomes.

RAS mutation status has important implications in treatment and prognosis of mCRC (Karapetis et al. 2008; De Roock et al. 2010; Sorich et al. 2015; Allegra et al. 2016). Several studies have demonstrated that RAS mutations are associated with a worse prognosis compared to RAS wild type cohorts (Sorbye et al. 2015; Sorich et al. 2015;

Vincenzi et al. 2015). This bears particular importance for regorafenib, which is the treatment in the control arm of this Phase III study. In the CORRECT study (regorafenib monotherapy for previously treated mCRC), subgroup analysis showed a treatment effect for OS in favor of regorafenib over placebo for patients with KRAS wild-type tumors whereas a numerically lower effect was reported in patients with KRAS-mutant tumors (Grothey et al. 2013). The HR (95% CI) of OS was 0.653 (0.476 to 0.895) for patients with KRAS wild-type tumors and 0.867 (0.670 to 1.123) for patients with KRAS-mutant tumors. Given that RAS mutation status has substantial prognostic significance, patients on this study will be stratified by their tumor RAS mutation status.

Time since diagnosis of first metastasis (< 18 months, ≥ 18 months) also will be used as a stratification factor. This stratification is commonly used when studying this patient population (Gothrey et al. 2014; Mayer et al 2015). The percent survival of mCRC patients is dramatically reduced from the first year from diagnosis to the second year from diagnosis of metastatic disease (Golan 2013; van der Geest 2015; Roder et al. 2015). Because time from diagnosis has great prognostic implications on survival, this trial will stratify accordingly.

In the mCRC setting, the natural frequency of tumors with MSI-high status is approximately 5% (Goldstein et al. 2014). In order to ensure generalizability of the study results, this Phase III study will limit the patients with MSI-high tumors to approximately 5%. Similarly, the frequency of extended RAS mutations in the previously treated mCRC patient population ranges from 50%–65%; thus, to reflect this prevalence, this study will enroll at least 50% mCRC patients with RAS-mutated tumors.

MSI status in CRC has important implications in both the treatment and prognosis for mCRC (Goldstein et al. 2014). In particular, recent data has shown that anti-PD-1 mAbs may be more efficacious in patients with MSI-high mCRC tumors (Le et al. 2015; Oh et al. 2015). Atezolizumab, an anti-PD-L1 mAb, inhibits the PD-L1 ligand, thereby blocking the interaction of PD-L1 with PD-1 and B7-1. Given that atezolizumab inhibits the interaction between PD-L1 and PD-1, patients with MSI-high mCRC tumors will likely experience differential efficacy compared to patients with microsatellite stable (MSS) mCRC tumors. In this study, the number of MSI-high patients will be capped at approximately 5% to represent the prevalence in this patient population. Stratification by MSI/MSS will not be necessary as the small number of MSI-high patients will likely not affect the overall results of the trial.

3.3.4 Rationale for Cobimetinib plus Atezolizumab Arm

Both nonclinical and clinical data from the Phase Ib Study GP28363 showed promising efficacy of cobimetinib plus atezolizumab in heavily pretreated KRAS-mutated mCRC patients. All the patients tested had MSI-stable tumors, unlike results from other checkpoint inhibitors (see Section 1.6). Because cobimetinib plus atezolizumab was well tolerated, and the efficacy data are promising, this combination will be further explored in this setting of high medical need.

3.3.5 Rationale for Atezolizumab Monotherapy Arm

Recent data showed that anti-PD-1 mAbs may be more efficacious in patients with MSI-high mCRC tumors (Le et al. 2015; Oh et al. 2015). In contrast to anti-PD-1 agents, atezolizumab is an anti-PD-L1 mAb, which is capable of inhibiting the interaction of PD-L1 with PD-1 and also PD-L1 with B7-1. Given that atezolizumab inhibits PD-L1 ligand from binding the PD-1 receptor and another immunomodulatory receptor (B7-1), the activity of atezolizumab may not be limited to MSI-high mCRC tumors. [REDACTED]

[REDACTED].
Therefore, the atezolizumab monotherapy was included in this Phase III study to further evaluate the activity of atezolizumab in mCRC.

3.3.6 Rationale for Regorafenib as Control Arm

Regorafenib and trifluridine/tipiracil are approved treatments for previously treated mCRC patients. Regorafenib was approved based on a Phase III trial that showed an improvement of OS compared to best supportive care of 1.4 months and a PFS of 0.3 months (Grothey et al. 2013). Regorafenib is approved in numerous countries worldwide, including the United States and European Union.

Trifluridine/tipiracil was recently approved in September 2015 in the United States. The approval was based on a Phase III trial demonstrating median OS improvement from 5.3 months with placebo to 7.1 months with trifluridine/tipiracil (Mayer et al. 2015).

As this is a global trial and regorafenib has been established as a standard of care treatment in patients in this setting in numerous countries, regorafenib is an appropriate treatment for the control arm.

The dosing and schedule for regorafenib that will be used in this study is the same as the dose that was used in the pivotal clinical trials (Grothey et al. 2013; Li et al. 2015) and the approved and marketed dose for this indication. Regorafenib will be administered at the recommended dose of 160 mg regorafenib (four 40 mg tablets) taken orally once daily for the first 21 days of each 28-day cycle.

3.3.7 Rationale for Dose and Schedule for Cobimetinib plus Atezolizumab and for Atezolizumab Monotherapy

In Arm A (cobimetinib plus atezolizumab), concomitant administration of atezolizumab and cobimetinib was studied in the Phase Ib Study GP28363. Cobimetinib 60 mg on a 21/7 schedule is the approved dose and schedule of cobimetinib. For administration with cobimetinib, on a 28-day cycle, a dose of 840 mg atezolizumab administered every 2 weeks has the equivalent dose exposure as the 1200 mg every 3 weeks (21-day cycle), the planned dose for the atezolizumab monotherapy arm. In Study GP28363, atezolizumab was dosed concurrently with cobimetinib at 800 mg IV q2w. The 840 mg dose is expected to be similar to the 800 mg dose of atezolizumab dose and selected in this study to simplify dose administration.

In Arm B (atezolizumab monotherapy), atezolizumab will be dosed at 1200 mg IV q3w. This is the dosing schedule that is being used in multiple Phase III studies of atezolizumab monotherapy across multiple tumor types. This dose and schedule of atezolizumab has been demonstrated to be safe and tolerable in over 1000 treated patients.

3.3.8 Rationale for Allowing Patients to Continue Treatment until Loss of Clinical Benefit

Conventional response criteria may not adequately assess the activity of immunotherapeutic agents as increase in tumor size does not consistently reflect therapeutic failure (Wolchok et al. 2009). The phenomena of pseudo progression or infiltration of tumor by immune cells may mimic tumor progression. Therefore, as this study is evaluating an immunotherapy, the study will allow patients to continue to receive study treatment after documented RECIST v1.1–defined radiographic disease progression, provided the benefit-risk ratio for the patient remains favorable as assessed by the physician and study monitor (see Section 4.3.2.4).

3.3.9 Rationale for Patient-Related Outcomes Assessments

The patient experience of mCRC includes impacts on symptoms (disease and treatment burden), functioning, and HRQoL. Disease-specific symptoms (e.g., bloating, abdominal pain, diarrhea, constipation, loss of appetite) and other symptoms (e.g., fatigue) that negatively impact patients' functioning and quality of life are relevant in this population. Patient-completed questionnaires are included to characterize the impact of disease and treatment on patients. The collection of this type of data will provide greater insights for both the medical and patient communities to understand disease and treatment burden and resulting HRQoL when patients are exposed to cobimetinib plus atezolizumab or atezolizumab monotherapy treatments in the mCRC setting (Marventano et al. 2013).

The EQ-5D-5L will be included to derive utility to inform pharmacoeconomic models.

3.3.10 Rationale for Collection of Archival and/or Fresh Tumor Specimens, Stratification Criteria, and Biomarker Assessments

Tumor tissue samples will be collected at baseline for genetic and histopathological assessments at DNA, RNA, protein, and tissue levels to add to researchers' understanding of disease pathobiology. Gene-based CRC classification increasingly has been proposed as a way of differentiating various subtypes of CRC and may have profound effects on both treatment and prognosis. These subtypes have been shown to have different immunomodulatory affects and may influence the efficacy of this combination (Guinney et al. 2015; Kocarnik et al. 2015; Lal et al. 2015). As these biomarkers may also have prognostic value, their potential association with disease progression will also be explored. Archival/baseline tumor analysis and classification of different CRC subtypes will be performed to further assess this possible relationship.

Tumor biopsies while on treatment and at progression are scheduled to further elucidate the possible mechanism of action or mechanisms of resistance (innate or acquired) of this regimen and may include evaluation of CD8-positive T-cell infiltrate, PD-L1 expression, and biomarkers of enhanced immune response, MAPK activation, and others involved in apoptosis or inflammation.

3.3.11 Rationale for Blood Sampling for Biomarker Assessments

An exploratory objective of this study is to evaluate biomarkers (including but not limited to cytokines, whole genome sequencing [WGS], cfDNA, and cancer-specific biomarkers, such as CEA) in blood samples. The evaluation of blood biomarkers may provide evidence for biologic activity of cobimetinib plus atezolizumab and atezolizumab monotherapy in patients with mCRC and may allow for the early prediction of clinical benefit of cobimetinib and atezolizumab use.

In addition, potential correlations of these biomarkers with the safety and activity of cobimetinib and atezolizumab will be explored.

3.3.11.1 Rationale of Optional Whole Genome Sequencing

Genomics is increasingly informing understanding of disease pathobiology and rationale for the development of new therapeutic approaches. WGS provides comprehensive characterization of the genome and, along with clinical data collected in this study, may increase the opportunity for making these discoveries.

Relevant literature on genomic analyses shows ample examples of genetic variations and their implications in immune responses. For instance, a recent report identified 20 genes linked to variability of the immune response to seasonal influenza vaccination, seven of which were shown to be involved in intracellular antigen transport, processing, and presentation ([Franco et al. 2013](#)). Similarly, genome-wide association studies (GWAS) have identified specific genetic variants that are associated with differences in WBC, neutrophil, and monocyte counts among individuals ([Knight 2013](#)). Furthermore, GWAS in autoimmune diseases have led to novel insights, an example of which is the role of autophagy in Crohn's disease, which was elucidated based on variation at two loci and has now become a major therapeutic target in this disease ([Hu and Daly 2012](#)).

It is also established that genetic variants of drug-metabolizing enzymes and transporters can affect the pharmacokinetics of drugs, which affects safety and efficacy. For example, patients who carry defective alleles of the gene encoding uridine diphosphate glucuronosyltransferase 1A1, which facilitates the metabolism and excretion of SN-38 (the active metabolite of irinotecan), are at a higher risk for adverse effects associated with the use of standard doses of irinotecan ([O'Dwyer and Catalano 2006](#)).

In addition to the link between genetic variation in drug-metabolizing enzymes and transporters and pharmacokinetics, recent studies have also identified genetic variants

that increase the likelihood of (or are protective of) developing drug-induced adverse events. For example, *HLA* has been demonstrated to play an important role in the development of drug-induced rash for some drugs (carbamazepine, abacavir, and allopurinol; Michels et al. 2015; Shirzadi et al. 2015; Stamp et al. 2015). In addition, mutations in *GSTP1*, *CTLA4*, and *FDG4* have been associated with development of drug-induced peripheral neuropathy of various small molecules (Lecomte et al. 2006; Ruzzo et al 2007; Favis et al. 2011; Baldwin et al. 2012).

Therefore, determining host genetic variation by performing WGS on patient samples collected in this study and assessing the relationship with response to treatment and observed adverse events may enable a further understanding of efficacy and safety for cancer immunotherapy and other therapeutic approaches. To this end, a blood sample may be collected from patients enrolled in this study for DNA extraction to enable WGS analysis. The WGS testing is an optional component of this study; patients can decline this sample collection and test.

WGS is contingent upon the review and approval by each site's IRB/EC and, if applicable, an appropriate regulatory body. If a site has not been granted approval for WGS, this assessment will not be applicable at that site.

4. MATERIALS AND METHODS

4.1 PATIENTS

Approximately 360 patients with unresectable locally advanced or metastatic CRC who have received at least two different chemotherapy regimens for metastatic disease will be enrolled in this study (see Section 4.5.2 for definition of chemotherapy regimen). The patients will be stratified for extended RAS status and time since diagnosis of first metastasis (<18 months vs. ≥18 months). MSI-high status will be capped at approximately 5%, and at least 180 patients with extended RAS will be enrolled in the study.

4.1.1 Inclusion Criteria

Patients must meet the following criteria for study entry:

Disease-specific inclusion criteria:

- Histologically confirmed adenocarcinoma originating from the colon or rectum (Stage IV American Joint Committee on Cancer [AJCC] 7th edition)
- Experienced disease progression on at least two prior systemic chemotherapy regimens for mCRC
 1. Prior systemic cytotoxic chemotherapy must include ALL of the following agents:
 - a) Fluoropyrimidines
 - b) Irinotecan
 - c) Oxaliplatin

2. Patients who have received prior anti-angiogenic therapy (e.g., bevacizumab) and/or anti-EGFR therapy (e.g., cetuximab) are eligible.
3. Patients must have had documented disease progression within 3 months of the last systemic therapy administration.
4. Patients who were intolerant to prior systemic chemotherapy regimens are eligible if there is documented evidence of clinically significant intolerance despite adequate supportive measures.
5. For patients who had disease recurrence within 6 months of completing adjuvant chemotherapy, the adjuvant regimen can be considered as one chemotherapy regimen for metastatic disease.

General inclusion criteria:

- Signed Informed Consent Form
- Age ≥ 18 years
- In the investigator's judgment, patient is able to comply with the requirements and assessments of the study protocol
- Eastern Cooperative Oncology Group (ECOG) performance status of 0 or 1 (see [Appendix 6](#))
- Anticipated life expectancy ≥ 3 months
- Able to comply with the requirements and assessments of the study protocol
- Adequate hematologic and end organ function, defined by the following laboratory results obtained within 14 days prior to first dose of study drug treatment:
 1. Hemoglobin ≥ 9 g/dL, platelet count $\geq 100,000/\text{mm}^3$, ANC $\geq 1500/\text{mm}^3$
 2. Creatinine clearance ≥ 30 mL/min
 3. Amylase and lipase $\leq 1.5 \times$ the upper limit of normal (ULN)
 4. Serum bilirubin $\leq 1.5 \times$ ULN; patients with known Gilbert's disease may have a bilirubin $\leq 3.0 \times$ ULN
 5. AST, ALT, and alkaline phosphatase (ALP) $\leq 2.5 \times$ ULN with the following exceptions:
 - a) Patients with documented liver metastases: AST and/or ALT $\leq 5 \times$ ULN
 - b) Patients with documented liver or bone metastases: ALP $\leq 5 \times$ ULN
 6. INR and PTT $\leq 1.5 \times$ ULN. Patients who are on therapeutic doses of anti-coagulants are eligible if they are on a stable dose of anti-coagulant for 28 days with stable INR and PTT values.

- Women of childbearing potential must agree to appropriately use an effective form of contraception (failure rate of < 1% per year) during the treatment period, within 5 months after the last dose of atezolizumab, and within 3 months after the last dose of cobimetinib and regorafenib.
 1. A woman of childbearing potential is defined as a sexually mature woman without prior oophorectomy or hysterectomy who have had menses within the last 12 months.
 2. A woman is not considered to be of childbearing potential if she has become amenorrheic for > 12 months and has a follicle-stimulating hormone level ≥ 40 IU/L.
- Men must agree not to donate sperm or have intercourse with a female partner without using appropriate barrier contraception during the treatment period and for 3 months after the last dose of either cobimetinib or regorafenib.
- Available and adequate baseline tumor tissue sample (archival or newly obtained biopsy; see Section 4.5.7)

4.1.2 Exclusion Criteria

Patients who meet any of the following criteria will be excluded from study entry:

Cancer-related exclusion criteria:

- After the approximate 5% cap for MSI-high patients is reached, only MSI-stable patients will be eligible.
- Once the 50% cap for wild-type RAS has been reached, only extended RAS-mutant patients will be eligible.
- Major surgery or radiotherapy within 21 days prior to Cycle 1 Day 1 or anticipation of needing such procedure while receiving study treatment.
- Treatment with any anti-cancer agent within 14 days prior to Cycle 1 Day 1
- Uncontrolled tumor-related pain. Patients requiring narcotic pain medication must be on a stable regimen at study entry.
 1. Symptomatic lesions (e.g., bone metastases or metastases causing nerve impingement) amenable to palliative radiotherapy should be treated prior to start of study treatment.
 2. Asymptomatic metastatic lesions whose further growth would likely cause functional deficits or intractable pain (e.g., epidural metastasis that is not presently associated with spinal cord compression) should be considered for loco-regional therapy if appropriate prior to the start of study treatment.
- Uncontrolled pleural effusion, pericardial effusion or ascites requiring repeated drainage more than once every 28 days. Indwelling drainage catheters (e.g., PleurX[®]) are allowed.
- Active or untreated CNS metastases are excluded. Patients with treated and asymptomatic CNS metastases are eligible, if they meet all of the following:
 1. Evaluable or measurable disease outside the CNS

2. No metastases to midbrain, pons, medulla, or within 10 mm of the optic nerves and chiasm
 3. No history or evidence of intracranial hemorrhage or spinal cord hemorrhage
 4. No evidence of clinically significant vasogenic edema
 5. Not on corticosteroids for ≥ 2 weeks; anti-convulsants at a stable dose are allowed.
 6. No evidence of clinical and radiographic disease progression in the CNS for ≥ 3 weeks after radiotherapy or surgery.
- Exclusion criteria related to study medication:
 1. Any cancer immunotherapy including CD137 agonists, anti-PD-1, anti-PD-L1, or anti-CTLA4
 2. Any MEK or ERK inhibitor
 3. Regorafenib
 - Patients with active malignancy (other than CRC) or a prior malignancy within the past 3 years are excluded. Patients with completely resected cutaneous melanoma (early stage), basal cell carcinoma, cutaneous squamous cell carcinoma, cervical carcinoma in-situ, breast carcinoma in-situ, and localized prostate cancer are eligible.

Exclusion criteria based on organ function or medical history:

Cardiovascular:

- Unstable angina, new onset angina within last 3 months, myocardial infarction within last 6 months and current congestive heart failure New York Heart Association Class II or higher.
- Left ventricular ejection fraction (LVEF) below institutional lower limit of normal or below 50%, whichever is lower.
- Poorly controlled hypertension, defined as a blood pressure consistently above 150/90 mmHg despite optimal medical management.

Infections:

- HIV infection
- Active tuberculosis infection
- Severe infections within 2 weeks prior to Cycle 1 Day 1
- Signs or symptoms of significant infection within 2 weeks prior to Cycle 1 Day 1
- Received oral or IV antibiotics within 2 weeks prior to Cycle 1 Day 1

Patients receiving prophylactic antibiotics (e.g., for prevention of urinary tract infection or chronic obstructive pulmonary disease) are eligible

- Active or chronic viral hepatitis B or C infection
 1. Patients with hepatitis B virus (HBV) infection are eligible if test for hepatitis B surface antigen (HBsAg) and HBV DNA are negative
 2. Patients with hepatitis C virus (HCV) infection are eligible if polymerase chain reaction (PCR) test for HCV RNA is negative.

Ocular:

- History of or evidence of retinal pathology on ophthalmologic examination that is considered a risk factor for central serous retinopathy, retinal vein occlusion, or neovascular macular degeneration
- Patients will be excluded if they currently have any of the following risk factors for retinal vein occlusion:
 1. Uncontrolled glaucoma with intra ocular pressure ≥ 21 mmHg
 2. Uncontrolled hypercholesterolemia > 300 mg/dL or 7.75 mmol/L
 3. Uncontrolled hypertriglyceridemia > 300 mg/dL or 3.42 mmol/L
 4. Fasting hyperglycemia > 160 mg/dL or 8.9 mmol/L

Autoimmune conditions and immunomodulatory drugs:

- History of autoimmune disease except for the following:
 1. Patients with autoimmune hypothyroidism on a stable dose of thyroid replacement hormone are eligible.
 2. Patients with controlled type 1 diabetes mellitus on a stable dose of insulin regimen are eligible.
- Patients with eczema, psoriasis, lichen simplex chronicus, or vitiligo with dermatologic manifestations only (e.g., patients with psoriatic arthritis) are permitted provided that they meet the following conditions:

Patients with psoriasis must have a baseline ophthalmologic exam to rule out ocular manifestations

Rash must cover less than 10% of body surface area

Disease is well controlled at baseline and only requiring low-potency topical steroids (e.g., hydrocortisone 2.5%, hydrocortisone butyrate 0.1%, flucinolone 0.01%, desonide 0.05%, aclometasone dipropionate 0.05%)

No acute exacerbations of underlying condition within the last 12 months (not requiring PUVA [psoralen plus ultraviolet A radiation], methotrexate, retinoids, biologic agents, oral calcineurin inhibitors, or high-potency or oral steroids)

- History of idiopathic pulmonary fibrosis, organizing pneumonia, bronchiolitis obliterans, drug-induced pneumonitis, or idiopathic pneumonitis

Patients with radiation pneumonitis within the radiation field are eligible.
- History of organ transplantation including allogeneic bone marrow transplantation

Other medical conditions or medications:

- Any hemorrhage or bleeding event CTCAE Grade 3 or higher within 28 days of Cycle 1 Day 1
- History of stroke, reversible ischemic neurological defect, or transient ischemic attack within 6 months prior to Day 1
- Proteinuria > 3.5 g/24 hours
- Serum albumin < 2.5 g/dL
- Foods, supplements or drugs that are potent CYP3A4 enzyme inducer or inhibitors are prohibited at least 7 days prior to Cycle 1 Day 1 and during study treatment. These include St. John's wort or hyperforin (potent CYP3A4 enzyme inducer) and grapefruit juice (potent cytochrome P450 CYP3A4 enzyme inhibitor).

General exclusion criteria:

- Inability to swallow medications
- Malabsorption condition that would alter the absorption of orally administered medications
- Pregnant, lactating, breastfeeding, or intending to become pregnant during the study
- History of severe hypersensitivity reactions to components of:
 1. Cobimetinib formulation
 2. Regorafenib formulation
 3. Atezolizumab formulation
- Administration of a live, attenuated vaccine within 4 weeks before randomization or anticipation of a live attenuated vaccine will be required during the study
- Any anti-cancer therapy, including chemotherapy, or hormonal therapy within 2 weeks prior to initiation of study treatment
- Treatment with systemic immunostimulatory agents (including but not limited to interferons, IL-2) within 4 weeks or 5 half-lives of the drug, whichever is shorter, prior to Cycle 1 Day 1
- Treatment with systemic immunosuppressive medications (including but not limited to prednisone, cyclophosphamide, azathioprine, methotrexate, thalidomide, and anti-tumor necrosis factor [TNF] agents) within 2 weeks prior to Cycle 1 Day 1

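### Protocol 4.1.2 names psoriatic arthritis as an example of permitted skin-only disease, contradicting its own limit and the autoimmune exclusion

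*Protocol*

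**What the plan says.** The autoimmune part of Protocol 4.1.2 opens with a broad exclusion, "History of autoimmune disease except for the following", followed by numbered exceptions for autoimmune hypothyroidism on stable replacement and controlled type 1 diabetes on stable insulin. A further bullet deals with eczema, psoriasis, lichen simplex chronicus and vitiligo. Its permission runs: "with dermatologic manifestations only (e.g., patients with psoriatic arthritis) are permitted". Four conditions are attached:

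- an eye check for one of the four diseases: "Patients with psoriasis must have a baseline ophthalmologic exam to rule out ocular manifestations"
- a rash area below 10% of the body surface
- a requirement on control and treatment: "Disease is well controlled at baseline and only requiring low-potency topical steroids"
- absence of any flare over the preceding 12 months, with a list of treatments that must not have been needed (among them methotrexate, biologics and oral steroids).

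The general exclusion criteria in the same section separately bar systemic immunosuppressive medication in the 2 weeks before Cycle 1 Day 1.

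The Protocol Synopsis repeats the same parenthetical. So does SAP Appendix 1, which reproduces the synopsis of protocol Version 4. The summary of changes for protocol Version 5 lists no edit to Section 4.1.2, so this is current text.

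**The concern.** The exception is confined to skin-only disease, yet the one example it gives is a joint disease. Grammatically, the parenthetical places psoriatic arthritis among the patients who may enter. The limit just before it, and the autoimmune exclusion above it, point the other way. A site has to choose which part of the sentence to follow.

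The criterion bears on safety. Protocol Section 5 presents the eligibility criteria as one of the measures that keep out patients at higher risk of toxicity, and Section 5.1.2 lists immune-related risks of atezolizumab, including hepatitis, pneumonitis, colitis and myocarditis. Two of the three arms receive atezolizumab.

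It also bears on reporting. Protocol 6.2 and SAP 4.2 call for major departures from the inclusion and exclusion criteria to be summarised by arm. With the sentence as it stands, nobody can say whether a randomized patient with psoriatic arthritis is such a departure.

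**Working it through.** No statistical figure is involved, so the check is a reading of the passages against each other.

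**Step 1: the limit against its example.** The limit admits the four listed conditions only when the disease shows itself in the skin alone. The example is a disease defined by joint involvement. A patient who fits the example fails the limit, so the two cannot both apply. Nothing else in the protocol or SAP explains or corrects the parenthetical.

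**Step 2: whether the other conditions settle the matter.** Take a hypothetical patient with a past diagnosis of psoriatic arthritis, no current joint symptoms and a small area of psoriasis controlled with a low-potency topical steroid.

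| Condition | Mentions joints? | This patient |
|---|---|---|
| Eye examination to rule out ocular disease | No | Can pass |
| Rash below 10% of body surface | No | Can pass |
| Controlled, low-potency topical steroids only | No | Can pass |
| No acute exacerbation in 12 months | No | Can pass |
| No systemic immunosuppressant in the prior 2 weeks | No | Can pass |

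Every condition can be met, so the conditions do not decide the case.

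**Step 3: the two readings.**
- Following the example, the patient is named as permitted and meets every listed condition, so the patient enters.
- Following the limit, the disease is not confined to the skin. The exception does not apply and the exclusion for a history of autoimmune disease does, so the patient stays out.

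Both readings rest on printed words in the same criterion.

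**Step 4: exposure if such a patient enters.** Planned allocation is about 180, 90 and 90 patients to Arms A, B and C. Arms A and B contain atezolizumab: (180 + 90) / 360 = 270 / 360 = 75%. A patient admitted on the permissive reading therefore has about a three in four chance of being assigned to atezolizumab.

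**Step 5: which copies matter.** Section 4.1.2 is the full statement of the criteria and the synopsis repeats it. SAP Appendix 1 is a copy of the Version 4 synopsis and governs no enrolment. The identical wording in three places makes a text-conversion fault an unlikely explanation.

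One layout feature is uncertain. The skin exception appears as its own bullet, not as a numbered item under the autoimmune exclusion. That may come from the PDF conversion, and it does not affect the conflict inside the sentence.

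**The case against.** The strongest reply is that the other conditions already do most of the work. A patient whose arthritis needs methotrexate, an anti-TNF agent or oral steroids would be stopped by the topical-only requirement, the exacerbation condition or the 2-week bar on immunosuppressants. A reader might infer from the parenthetical that sites may enrol patients with active systemic autoimmune disease. The documents do not support that: even on the permissive reading, the only patients admitted are those whose disease is controlled with nothing beyond low-potency topical steroids. This part of the reply stands and narrows the point. It does not remove it, because no condition speaks to joint disease and the patient in Step 2 remains undecided.

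A reader might also infer that the study population would differ materially between sites, or that the survival comparison could be biased. Neither is shown. Protocol 9.4 foresees about 75 centres, and the number of such patients among roughly 360 is likely small. Eligibility is settled before randomization (Protocol 4.2), and efficacy is analysed in all randomized patients by assigned arm. The error rate, power and event counts are untouched.

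Finally, there are procedures for eligibility. The investigator confirms all criteria before randomization (Protocol 4.5.1). Under Protocol 9.2, waivers are not allowed and the sponsor reviews all deviations. These help only when the criterion has one meaning. A reviewer who has to class the patient in Step 2 faces the same two readings as the site did.

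**Conclusion.** The point holds as an internal inconsistency in an operative eligibility criterion. The example and the limit in one sentence of Protocol 4.1.2 cannot both be followed, the general autoimmune exclusion conflicts with the example, and no other text resolves it. The wording is worth correcting because the criterion is safety-relevant and the correction is cheap.

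Its size is modest. The patients in question are those with quiet psoriatic arthritis and limited skin disease. The documents give no prevalence, so that they are few is a judgement and not a calculated figure. What follows is that sites may apply the criterion differently and that deviations of this kind cannot be classed with confidence. No effect on any endpoint is claimed.

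The conclusion rests on reading psoriatic arthritis in its ordinary sense, as disease that involves the joints. It does not rest on any view of whether such patients ought to be enrolled. The documents do not show whether the example or the limit is the slip, and that is for the sponsor to settle.

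**What to change.** Reconcile the parenthetical with the skin-only limit and with the autoimmune exclusion, in Protocol 4.1.2 and in the Protocol Synopsis, so that the criterion gives one answer for a patient with psoriatic arthritis. Carry the result into SAP Appendix 1 when that reproduction of the Version 4 synopsis is next updated.

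If patients have already been randomized under the present wording, a short clarification of how the criterion is to be applied would let such cases be classed the same way in the deviation summaries of Protocol 6.2 and SAP 4.2.

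The cost is a wording change through the usual amendment process. The analyses, sample size and timing do not change.
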